Bioscience Industrial Group	and safety o	of Immune Globulin Intravenous (Human)Flebogamma® t	§ 5% DIF in pat	tients with Post-Po	st-Polio Syndr	ome	rage	20 01 122

hours following the completion of the infusion of the total dose of investigational product on the last day, will be summarized and listed. In addition, AEs temporally associated to the infusion of the investigational products for which the incidence in the Flebogamma[®] 5% DIF exceeds the incidence in the placebo group will also be summarized separately.

Subjects who have a serious adverse event (SAE) or who withdraw from the study because of an AE will also be individually listed and summarized.

AEs for which the investigator causality assessment is missing or undetermined will be individually listed.

Vital signs (T, RR, HR, SBP and DBP) will be listed for each subject. In case a subject presents with a clinically relevant abnormality of vital signs during an infusion, the event will be flagged and reported as an AE temporally associated to the infusion. For each subject and for each infusion, each of the 5 vital signs will be considered.

[figure not shown]
Physical findings (normal and abnormal) will be listed for each clinical trial subject. Any clinically relevant abnormality developed by individual during the clinical trial and not already present at baseline will be reported as an AE.

All clinical laboratory data for renal (creatinine, BUN and GFR), hepatic (ALT, AST, ALP and TBL) and haematological parameters (CBC including differential leukocyte count) will be listed for each clinical trial subject. The Investigator will be required to classify laboratory results out of the normal range reported by the laboratory as clinically relevant or not according to his/her judgment. Laboratory results out of the normal range judged by the Investigator as clinically relevant will be reported as AEs.

A formal unblinded interim analysis will be performed to select 1 of the 2 doses for Stage 2 based on the primary efficacy endpoint of 2MWD. The interim analysis will be performed when at least 80% of randomized subjects have finished the treatment period of Stage 1. Based on the interim analysis results, the independent DMC will use the pre-specified dose selection rule to select 1 of the Flebogamma doses (2 g/kg or 1 g/kg) to continue the Stage 2 of the clinical trial. The following dose selection rules will be applied:

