AEs temporally associated to the infusion of the investigational products (*i.e.*, infusional AEs, including infusional suspected ADRs), will be summarized by presenting infusion/subject incidences and percentage and ordered by ordinal number of infusions, and listed. In addition, the infusion rate in effect at the time of onset of the AE, the time the AE is first reported, and the time the AE changes materially in intensity and/or resolves will be also reported and listed. In addition, AEs temporally associated to the infusion of the investigational products for which the incidence in the Flebogamma[®] 5% DIF exceeds the incidence in the placebo group will be summarized separately.

Subjects with a serious adverse event (SAE) or who withdraw from the study because of an AE will also be individually listed and summarized.

AEs for which the investigator causality assessment is missing or undetermined will be individually listed.

Vital signs during infusions:

Vital signs (T, RR, HR, SBP and DBP) will be listed for each clinical trial subject. In case a subject presents a clinically relevant abnormality of vital signs (based on the Investigator's judgment) during an infusion, the event will be flagged and reported as an AE temporally associated to the infusion. All vital signs will be evaluated for each subject and for each infusion.

Physical assessment:

Physical findings (normal and abnormal) will be listed for each clinical trial subject. Any clinically relevant abnormality (based on the Investigator's judgment) developed by individual during the clinical trial and not already present at baseline will be reported as AE.

Blood biochemistry and cell counts:

All clinical laboratory data for renal (creatinine, BUN and GFR), hepatic (ALT, AST, ALP and TBL) and haematological parameters (CBC including differential leukocyte count) will be listed for each clinical trial subjects. Laboratory results out of the normal range judged by the Investigator as clinically relevant will be considered AEs.

	Number	GLB-PRT-FLB-IG1104	Version	7.0	Status	Effective	Effective Date	07-Mar-2022
CIVILOLS	IG1104 - A n	multicenter, prospective, randomized, placebo-controlled,	, double-blind	l, parallel-gro	up clinical trial	to assess the efficacy		70 F 3 - 00 F
Bioscience Industrial Group	and safety or	of Immune Globulin Intravenous (Human) Flebogamma®	5% DIF in pa	tients with P	ost-Polio Syndı	ome	rage	108 01 122

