4.2 Safety Variables

The following safety variables will be assessed:

- Adverse Events (AEs), adverse reactions (ARs), suspected adverse drug reactions (ADRs), serious AEs (SAEs), AEs leading to the discontinuation of the study, AE with special interest (AESI), and infusional AEs. Section 11.1 provides definitions of AE endpoints.
- Blood biochemistry (creatinine, blood urea nitrogen (BUN), alanine aminotransferase (ALT), aspartate aminotransferase (AST), alkaline phosphatase (AP) and total bilirubin (TB)) and cell counts (complete blood count (CBC), including differential leukocyte count)
- Vital signs (heart rate, blood pressure, respiratory rate, and temperature)
- Physical assessments

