5 GENERAL STATISTICAL CONSIDERATIONS

Statistical analyses and data presentations will be generated using SAS version 9.2 or higher.

Unless otherwise noted, for continuous variables, descriptive statistics will include the number of non-missing values, mean, standard deviation, median, minimum and maximum. The minimum and maximum will be presented to the same number of decimal places to which the data were recorded, the mean and median will be presented to 1 decimal place more than the data were recorded and the standard deviation will be presented to 2 decimal places more than the data were recorded.

For categorical variables, descriptive statistics will include counts and percentages per category. Percentages will be presented to 1 decimal place. Percentages of 0 and 100 will be reported as whole numbers (i.e. "0%" and "100%", respectively).

Unless otherwise noted, all statistical inference will be tested at 2-sided with α =0.05. P-values will be presented to 4 decimal places and confidence intervals will be presented to the same number of decimal places as the corresponding point estimate.

Unless otherwise noted, all data collected in the electronic case report forms (eCRFs) or electronically transferred (such as central laboratory data) will be presented in data listings. Subjects will be identified in the data listings by subject number (which includes site number)

and grouped by treatment arm. All summaries and listings will be presented by treatment arm and by study stage (i.e., Stage 1, Stage 2, and Overall) if appropriate.

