6 SUBJECT DISPOSITION

Subject disposition will include the number of subjects screened, number of randomized subjects, number and percentage of subjects in each analysis population, number and percentage of subjects completing the scheduled treatment of investigational products, number and percentage of subjects completing the study treatment period up to Week 52, and number and percentage of subjects completing the study follow-up period up to Week 76 by treatment arm and by study stage.

The number and percentage of subjects discontinuing early from the study will be summarized for primary reasons of discontinuation. Also, the number and percentage of screening failures will be summarized for primary reasons of ineligibility in a separate table.

Disposition status will be listed for all subjects.

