11.1 Adverse Events

Analysis of AEs will be primarily focused on a descriptive analysis of AEs, suspected adverse drug reaction (ADRs) and adverse reaction (AR). Safety assessment will be based on the prevalence of suspected ADRs and AR occurred during the clinical trial.

- Suspected ADRs are defined as AEs with a causal relationship to study treatment of "Definitely Related", "Probably Related", "Possibly Related" or "Doubtful/Unlikely Related".
- ARs are defined as AEs with a causal relationship to study treatment of "Definitely Related".

AEs will be classified according to their onset date/time into the following categories:

Treatment emergent AEs (TEAEs): AEs with an onset date/time between first study treatment date/time and final study visit date or a pre-existing AE that worsens in severity within the same time window.

TEAEs will be further classified as follows:

- o On-treatment TEAEs: TEAEs with an onset date/time between first study treatment date/time and last study treatment date +4 weeks.
- o Infusional TEAEs: TEAEs with an onset date/time between the start date/time of study treatment infusion and 72 hours post-completion of the infusion of total dose of study treatment during any of the 2-day infusion periods.
- Post-treatment TEAEs: TEAEs with an onset date/time after the last study treatment date/time +4 weeks.
- non-TEAEs: all other AEs i.e. AE which occur prior to the start of study treatment.

For the purposes of classifying AEs into the above categories, partial AE start and end dates will be imputed to allow comparison with the study treatment date start and end dates. Section 13.1.1 below presents the imputation rules. Note, the imputed dates will be used for classification purposes only and the original partial AE dates will be presented in data listings.

AEs will be coded using MedDRA dictionary version 17.1 and summarized (stage 1 and stage 2 combined) by treatment group, system organ class (SOC) and preferred term (PT) as follows:

- TEAEs:
 - On-treatment TEAEs
 - overall
 - by maximum severity
 - by maximum causal-relationship
 - **SAEs**
 - suspected ADRs
 - ARs
 - **AESIs**
 - suspected ADRs of Special Interest (SI),
 - ARs of SI

- o Post-treatment TEAEs
 - overall
 - SAEs
- Infusional TEAEs
 - overall
 - SAEs
 - suspected ADRs
- Non-TEAEs

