Adverse events will be summarized by presenting, for each treatment group, the number and percentage of patients with any AE, any AE within each SOC and any AE within each PT (grouped by SOC).

For summaries by maximum severity, if a patient reported more than one AE with the same PT, the AE with the maximum severity will be presented. If the severity of an AE is missing, the severity will be treated as missing in summaries. If a patient reported more than one AE within the same SOC, the patient will be counted only once under the maximum severity within the SOC.

Corresponding reporting rules will be applied for summaries by maximum causal-relationship.

All AEs will be listed by treatment group and subject identifier. In addition, subjects with SAEs and AEs leading to premature discontinuation of treatment period from the study will be individually listed.

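### SAP 11.1 omits, without declaring it, the protocol's per-infusion summary of infusional AEs and its summary of subjects who withdraw because of an AE

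*SAP*

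**What the plan says.** **Protocol.** Section 10.1.3 says that infusional AEs will be "summarized by presenting infusion/subject incidences and percentage and ordered by ordinal number of infusions". The same section says: "Subjects with a serious adverse event (SAE) or who withdraw from the study because of an AE will also be individually listed and summarized". The synopsis repeats the second commitment, for subjects "who withdraw from the study because of an AE will also be individually listed and summarized".

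**SAP.** Section 4.2 names "AEs leading to the discontinuation of the study" among the safety variables and refers to Section 11.1 for definitions of the AE endpoints. Section 11.1 then says that AEs will be "summarized (stage 1 and stage 2 combined) by treatment group, system organ class (SOC) and preferred term (PT) as follows". The list that follows has three headings for treatment-emergent events (on-treatment, post-treatment, infusional) and one for non-treatment-emergent events. Infusional events have three entries: overall, SAEs and suspected ADRs. The counting rule for all AE tables is the number and percentage of patients. Nothing in the list covers events leading to discontinuation; the only output for them is a listing: "subjects with SAEs and AEs leading to premature discontinuation of treatment period from the study will be individually listed".

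SAP 12, which records changes from the protocol's analyses, contains one item, on cytokine testing.

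**The concern.** The SAP is based on protocol version 7.0. Its revision history says that version 3.0 clarified how the AE summaries are broken down. The list in 11.1 is therefore the current specification, and it can be expected to be programmed as written.

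Both omitted summaries bear on how well repeated infusion is tolerated. The product is given every 4 weeks at up to 13 visits. For such a schedule, a reader wants to know how often an infusion is followed by a reaction, and whether this changes from the first infusion to later ones. The protocol's format answers that; a count of patients who ever had a reaction does not. For AEs that end participation, a reader wants to know which events they were in each arm. The listing holds that information, but no table presents it.

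**Working it through.** No figure in the plan has to be reproduced. The check compares what each document commits to, with one short calculation.

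**1. Infusional AEs**

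| | Protocol 10.1.3 | SAP 11.1 |
|---|---|---|
| Unit counted | infusions and subjects | patients |
| Order | by infusion number | by system organ class and preferred term |
| Output | summary and listing | three patient-count tables; all AEs listed |

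What the patient count loses can be bounded. Inputs: up to 13 infusion visits per subject (protocol 4.4.2.3 and 7.1) and 42 planned subjects per arm in Stage 1 (protocol 10.2). Assume every visit is attended.

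- One subject: a single reaction is 1/13 = 7.7% of visits; a reaction every time is 13/13 = 100%. In the patient table each counts as 1.
- One arm: visits = 42 × 13 = 546. If *k* subjects ever react, patient incidence is *k*/42 whatever the frequency. Per-visit incidence lies between *k*/546 (one reaction each) and 13*k*/546 = *k*/42 (a reaction every time).

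The same patient percentage is thus compatible with per-visit rates that differ by up to a factor of 13. This is a bound on what the table cannot distinguish. It is not a forecast of a difference between arms.

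**2. Withdrawals because of an AE**

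- The protocol sentence pairs SAEs with AE withdrawals and asks for both to be listed and summarised. SAP 11.1 tabulates SAEs and lists them. AE withdrawals are only listed.
- Of the AE variables named in SAP 4.2, the others (AEs, ARs, suspected ADRs, SAEs, events of special interest, infusional AEs) each have at least one table in 11.1. Events leading to discontinuation have neither a table nor a definition there. This looks more like an oversight than a decision.
- SAP 6 offers a partial substitute: "The number and percentage of subjects discontinuing early from the study will be summarized for primary reasons of discontinuation". SAP 5 sets the layout: "All summaries and listings will be presented by treatment arm and by study stage (i.e., Stage 1, Stage 2, and Overall) if appropriate". Together these probably give a by-arm count of withdrawals attributed to an AE.
- That substitute has limits. It uses the primary reason only and carries no event term, severity or causality. The SAP does not print the reason categories. Protocol 6.3 lists confirmed thromboembolic events and clinically significant hemolysis (items 6 and 7) separately from AEs in general (item 5), so those withdrawals may fall outside an AE row. The same table will also hold discontinuations caused by the sponsor's early termination (SAP 2).

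**3. Declaration.** SAP 12 mentions neither difference.

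**The case against.** The strongest case on the other side has four parts.

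- **Tolerability is compared between arms.** A reader might infer from these gaps that tolerability of the two doses is not tabulated against placebo. The documents do not support that. SAP 11.1 plans on-treatment events overall, by severity and by causality, with SAEs, suspected ADRs, ARs and events of special interest, plus infusional events, all by treatment group. This part stands in full.
- **AE withdrawals are probably counted by arm already.** SAP 6 with SAP 5 most likely does this, and protocol 5.4 requires the reasons for withdrawal in the eCRF. It would therefore be wrong to say that their rate is not compared between arms. This stands, provided that AE is one of the reason categories.
- **The protocol prescribes no format for the withdrawal summary.** It speaks of subjects being summarised, not of a table by organ class and term. A listing plus a count by reason could be said to meet the wording. This has force: the organ-class format is good practice, not a protocol requirement. It does not explain why a variable named in SAP 4.2 is left without a definition or an AE-based summary.
- **Any subject-level incidence table hides repetition, and no data are lost.** All AEs are listed, and SAP 9.3 summarises the number of infusions received. That is true, but here the protocol itself asks for the per-infusion view, so its absence is a departure from the protocol rather than a reviewer's preference.

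**Conclusion.** The point holds as a reporting gap between protocol and SAP. The per-infusion part is the firmer of the two: the protocol states the unit and the ordering, SAP 11.1 provides neither, and the change is undeclared. The withdrawal part is weaker. A summary was promised and only a listing is planned in 11.1, but the disposition table probably fills part of the gap. That rests on the assumption that AE appears as a primary-reason category, which the SAP does not confirm.

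The size is small. Two descriptive summaries are missing; for infusional events, the tables as planned cannot distinguish per-visit rates up to 13-fold apart. Safety analysis in this trial is descriptive, and the primary analysis, the type I error and the dose-selection rule are unaffected.

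**What to change.** In SAP 11.1 add:

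- **(a) Infusional events per infusion.** Number and percentage of infusions with at least one infusional event, overall and by infusion number, by arm. State the unit. The infusional window in both documents covers the 2-day infusion period plus 72 hours, so the infusion visit (up to 13 per subject) fits better than the single infusion day (up to 26). The denominator should be infusions actually given.
- **(b) Events leading to discontinuation.** A by-arm summary of treatment-emergent AEs leading to discontinuation. System organ class and preferred term is the natural format, since it matches the other AE tables. Define the set of events, and say that thromboembolic and hemolysis withdrawals are included.

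If either summary is left out on purpose, say so in SAP 12 with a reason.

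The cost is two descriptive tables and a few lines of SAP text. The inputs are already collected: AE onset and action taken (protocol 9.3.8), infusion records (protocol 7.3) and withdrawal reasons (protocol 5.4).

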11.2 Laboratory Assessments

Blood biochemistry and cell counts data will be collected at the assigned visits according to the protocol and will be stored and/or testing performed by a central laboratory.

The lab parameters will be summarized using number of subjects, mean, standard deviation, median, minimum, and maximum values at each visit for continuous variables, and counts and percentages for categorical variables. Change from baseline to each scheduled post-baseline visit will be summarized for each continuous variable. Shift tables, based on the high/low flags, will also be summarized for each parameter at each visit.

All laboratory data will be presented in data listings.

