In the final formulation, Flebogamma[®] 5% DIF contains 5 g human normal immunoglobulin and 5 g D-sorbitol (as stabilizer) in 100 mL of water for injection. Patients with very rare hereditary problems of fructose intolerance must not take this medicine. In case of inadvertent application and suspicion of hereditary fructose intolerance the infusion has to be stopped immediately, normal glycaemia has to be re-established and organ function has to be stabilized by means of intensive care.

As with all products containing human origin proteins, hypersensitivity reactions, or allergic reactions, cannot be rejected, including severe anaphylactic reactions (anaphylactic shock) with the IVIG administration.

Adverse reactions (ARs) associated with IVIG administration such as chills, headache, dizziness, fever, vomiting, allergic reactions, nausea, arthralgia, low blood pressure and moderate low back pain may occur occasionally. Rarely IVIG may cause a sudden fall in blood pressure, bronchitis, cough, wheezing, dyspnea, flushing, chest pain, diarrhea, hepatic enzymes increase, abdominal pain, decrease in blood cell counts, muscle pain, muscle cramp and, in isolated cases, anaphylactic shock, even when the patient has shown no hypersensitivity to previous administration. Cases of reversible aseptic meningitis, reversible haemolytic reactions, especially in those patients with blood groups A, B, and AB, and in isolated cases of reversible haemolytic anaemia/haemolysis, requiring transfusion and rare cases of transient cutaneous reactions (including cutaneous lupus erythematosus – frequency unknown), have been observed with IVIG. Increase in serum creatinine level and/or occurrence of acute renal failure have also been observed. Very rarely, thromboembolic reactions such as myocardial infarction, stroke, pulmonary embolism (PE), deep vein thrombosis (DVT), severe allergic cutaneous reactions and transfusion related acute lung injury (TRALI) have been reported [6].

All patients, but especially individuals receiving IVIG for the first time or being restarted on the product after a treatment hiatus of more than 8 weeks, may be at a higher risk for the development of fever, chills, nausea, and vomiting. Careful monitoring of recipients and adherence to recommendations regarding dosage and administration may reduce the risk of these types of events.

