- 19. Subjects with renal impairment (*i.e.*, serum creatinine exceeds more than 1.5 times the upper limit of normal [ULN] for the expected normal range for the testing laboratory).
- 20. Subjects with AST or ALT levels exceeding more than 2.5 times the ULN for the expected normal range for the testing laboratory.
- 21. Subjects with hemoglobin levels <10 g/dL, platelets levels <100,000 /mm³, white blood cells count <3.0 k/ μ L and ESR >50 mm/h or twice above normal.
- 22. Subjects with known seropositive to HCV, HIV-1 and/or HIV-2.
- 23. Subjects with a history of intolerance to fructose.

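### No table in SAP 11.2 counts subjects by worst renal or hepatic value, so worsening from an already abnormal baseline, or within the normal range, does not register as a shift

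*SAP*

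**What the plan says.** SAP 11.2 sets out the laboratory summaries in three sentences. First, "The lab parameters will be summarized using number of subjects, mean, standard deviation, median, minimum, and maximum values at each visit" for continuous variables. Second, "Change from baseline to each scheduled post-baseline visit will be summarized for each continuous variable". Third, "Shift tables, based on the high/low flags, will also be summarized for each parameter at each visit". It closes with "All laboratory data will be presented in data listings". SAP 11.2.1 marks creatinine, GFR, ALT, AST, alkaline phosphatase and total bilirubin for summary. SAP 5.1 sends results from unscheduled visits to listings only.

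There is a second tabulated route. Protocol 10.1.3 states that "Laboratory results out of the normal range judged by the Investigator as clinically relevant will be considered AEs", and SAP 11.1 states that "Adverse events will be summarized by presenting, for each treatment group, the number and percentage of patients with any AE", broken down by system organ class and preferred term.

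Two other parts of the protocol bear on the point:

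- Protocol 2.3 lists hepatic enzyme increase among the known effects of IVIG and says of the kidney: "Increase in serum creatinine level and/or occurrence of acute renal failure have also been observed".
- Protocol 6.2 sets the entry limits. Criterion 19 excludes "Subjects with renal impairment (*i.e.*, serum creatinine exceeds more than 1.5 times the upper limit of normal [ULN"]. Criterion 20 places the AST/ALT limit at 2.5 x ULN. Values between ULN and those limits are therefore eligible.

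**The concern.** The shift table is the only planned laboratory table that sorts subjects into categories, and it has two blind regions. It cannot show worsening in someone who is already outside the range at baseline, and it cannot show a proportionate rise that ends inside the range. Because it is produced visit by visit, it also does not say how many different subjects in an arm ever worsened.

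The protocol names kidney and liver effects as risks of the product. A reader of the study report would expect to see how many subjects per arm had a rise of a given size. Under the present plan that count has to be built by hand from listings.

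**Working it through.** Neither document states a figure for laboratory flagging, so there is none to reproduce. The check has four steps.

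**1. Subjects abnormal at baseline.** Inputs: the entry limits in Protocol 6.2, the baseline definition in SAP 5.1 (the Enrollment Visit/Infusion Visit 1 value), and flags with three levels (low, normal, high), as the SAP wording implies. The fold-rises are illustrations.

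- Creatinine at 1.5 x ULN rising 1.5-fold: 1.5 x 1.5 = 2.25 x ULN. Shift cell: High-to-High.
- ALT at 2.5 x ULN rising 3-fold: 2.5 x 3 = 7.5 x ULN. Shift cell: High-to-High.
- GFR already flagged Low and falling further: Low-to-Low. Protocol 4.4.4.3 provides for infusing subjects with abnormal GFR, so this case is foreseen.

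This step needs no assumption about how baselines are distributed.

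**2. Rises that end inside the range.** A k-fold rise is unflagged when k x baseline ≤ ULN, that is, when baseline ≤ ULN/k. For k = 1.5 the cut is 0.667 x ULN; for k = 2 it is 0.5 x ULN.

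The share of subjects below the cut depends on a baseline distribution and a reference range that the documents do not give. As an assumption, take baselines as normal with mean m and SD s, in units of ULN. The share unflagged after a 1.5-fold rise is Φ((0.667 − m)/s).

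(a) Baselines fill the reference range, with r = LLN/ULN, m = (1 + r)/2 and s = (1 − r)/(2 x 1.96):

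| r | 0.3 | 0.4 | 0.5 | 0.6 | 0.7 |
|---|---|---|---|---|---|
| Share unflagged | 54% | 41% | 26% | 10% | 1% |

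(b) Mean baseline set directly, with s = 0.15:

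| m | 0.50 | 0.60 | 0.65 | 0.70 | 0.80 |
|---|---|---|---|---|---|
| Share unflagged | 87% | 67% | 54% | 41% | 19% |

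These ten settings run from about 1% to 87%. They illustrate and do not bound the answer: with s = 0.10 at m = 0.50 the share is 95%. Under a symmetric distribution, the share passes 50% only if the centre of the baselines lies below 0.667 x ULN.

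**3. Per-visit display against per-subject counts.** Protocol 4.5.2.7 schedules the renal and hepatic panel at Weeks 12, 24, 36 and 52 in the treatment period and at Weeks 64 and 76 in follow-up. Suppose each treatment-period visit shows a 2% shift rate (assumed). The share of subjects ever shifting over four visits is:

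- 2% if the same subjects shift each time;
- 1 − 0.98^4 = 7.8% if visits are independent;
- 4 x 2% = 8% if different subjects shift each time.

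Over all six visits, independence gives 1 − 0.98^6 = 11.4%. The per-visit tables do not distinguish these cases.

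**4. What the other summaries add.** One subject with a 50% rise, from a baseline equal to the arm mean, moves that mean by 0.5/42 = 1.2% in a Stage 1 arm of 42, or 0.5/84 = 0.6% in a planned two-stage pooled arm of 84. The mean therefore shows little. The per-visit maximum of the change does show the single largest rise, but not how many subjects lie behind it. The adverse-event tables do count subjects, but only when the value is out of range and the investigator judges it clinically relevant.

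**The case against.** The strongest reply is that the plan already shows a good deal:

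- SAP 11.2 tabulates minimum and maximum at each visit. By the general convention in SAP 5, change from baseline is summarized with its own minimum and maximum. A large rise in one subject, including one who starts High, would appear there.
- Adverse events are counted per subject across the period, by arm, with on-treatment tables by severity and causal relationship. A subject already High who rises further is out of range, so this route is open. SAP 11.1 also counts a pre-existing event that worsens as treatment-emergent.
- GFR is summarized as well, so a creatinine rise may appear there as a Low flag.
- All values are listed, and the protocol itself promises no more than listings and adverse-event reporting for these parameters.

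All of this is correct, and it rules out several stronger readings. A reader might infer that laboratory harm is shown only as mean changes and flag shifts, or that the shift table is the only categorical display of renal or hepatic harm. The maxima and the adverse-event tables contradict both. A reader might infer that a 1.5-fold creatinine rise usually goes unflagged. The documents give no reference range or baseline distribution, and step 2 shows shares on both sides of 50%. A reader might judge dilution of means at about 42 per arm throughout, but SAP 11 pools safety data across stages. Nor do the documents say how many subjects entered High, or that these are the subjects at greatest renal risk. Protocol 4.4.4.3 lists several predispositions, such as age over 65 and diabetes, that do not require a high creatinine.

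What the reply does not remove is the missing count. Maxima do not say how many subjects are affected. The adverse-event route rests on judgment and excludes in-range rises. A GFR already Low cannot shift further. Listings leave the tabulation to the reader.

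**Conclusion.** The point stands as a cheap improvement to safety reporting. No planned table counts subjects per arm by worst post-baseline value, fold-change from own baseline, or multiple of ULN. Further worsening from a High baseline (or a Low one for GFR) is invisible to the shift table by construction, given three-level flags. A 1.5-fold creatinine rise can also go unflagged when baseline is at or below two-thirds of ULN.

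The number of subjects affected cannot be derived from the documents; about 1% to 87% for the in-range case reflects assumed baselines only. For the liver the gap is structural, and no frequency is offered.

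The early termination described in SAP 2 does not change this, because SAP version 3.0 still plans full safety reporting. Sample size, type I error, power and the primary analysis are not touched.

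**What to change.** Keep the flag shift tables in SAP 11.2 and add the following for creatinine, GFR, ALT, AST and total bilirubin:

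1. By-arm counts and percentages of subjects by worst post-baseline value, using scheduled and unscheduled results. Grade by fold-change from the subject's own baseline (percentage fall for GFR) and by multiple of ULN (not for GFR).
2. A shift table from baseline to worst post-baseline value.

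Fix the reporting cut-points before unblinding. They are display categories only; no dosing, stopping or eligibility rule changes.

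The cost is SAP wording and about two extra tables from laboratory data already collected. One limit remains. The renal and hepatic panel is drawn before infusion and at intervals of at least 12 weeks, so a worst-value table would still miss short-lived post-infusion changes that no sample captured.
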